9.3.1. SAE form criteria

All SAEs that occur from the administration of the ICG to patient (for intervention arm patients) or from surgery (for control and intervention arm patients) up until the 12 month follow up visit must be documented by research staff at site. SAEs should be documented on an SAE form and emailed to the NCTU (i.e., [contact]) via secure email or other secure email as per site policies as soon as it is available or at least within 24 hours of the information becoming available. SAEs will be logged by the NCTU team on the trial safety database and will be given a unique SAE number. The reporting site will be sent confirmation of receipt of the SAE from NCTU. Events will be followed up until the event has resolved or a final outcome has been reached.

See Section 16.1, Appendix 1 for the Safety Reporting Diagram.

9.4. Recording and Reporting Related Serious Events (RSE)

All RSEs occurring as determined using the SAE Report Diagram (see Section 16.1, Appendix 1) occurring from the administration of the ICG to patient up until the 12 month follow up must be reported to the NCTU on an SAE form.

The assessment of expectedness as indicated on the SAE form will be reviewed and confirmed by the CI against the details of the SmPC for ICG.

Unexpected Related Serious Events (URSE) must be reported no later than 15 calendar days after the NCTU has first knowledge of the event to the NHS REC. Any relevant follow-up information should be sought and reported as soon as possible after the initial report.

As soon as a site suspects that a RSE may be a URSE they must contact the CI, sponsor representative and the trial manager immediately. The reporting timeframe starts at day 0 when the NCTU is in receipt of a minimum set of information:

- Sponsor trial reference and trial name (sponsor reference)
- Patient trial number and date of birth
- Name of intervention
- Date of notification of the event
- Medical description of the event
- Date and time of the onset of the event (including event end date if applicable)
- Causality assessment
- Seriousness of the event, particularly if life threatening or fatal
- An identifiable reporter (e.g., Principal Investigator)

This information must be provided via secure email (e.g., NHS.net). The site is expected to fully cooperate with the NCTU in order that a full and detailed report can be submitted to the NHS REC within the required timelines.

PIs will be informed of all URSEs by the NCTU.

9.5. Responsibilities

9.5.1. Principal Investigator (or delegated person at site)

- Checking for relevant AEs and complications at four time points: day of resection,1-, 6- and, in the case of complications only 12- month follow up visits.
- Completing complications eCRF at four time points: day of resection and 1-, 6and 12- month follow up visits.
- Using medical judgement in assigning seriousness and causality and providing an opinion on expectedness of events.
- Ensuring that all SAEs and RSEs, including URSEs, are recorded and reported to the NCTU within 24 hours of becoming aware of the event and provide further follow-up information as soon as available.
- Ensuring that relevant AEs and complications are recorded in line with the requirements of the protocol.

9.5.2. Chief Investigator

- Clinical oversight of the safety of trial participants, including an ongoing review of the risk/benefit.
- Using medical judgement in assigning seriousness, causality, and expectedness of SAEs where it has not been possible to obtain local medical assessment.
- Using medical judgement in assigning expectedness to RSEs.
- Immediate review of all URSEs.
- Review of reported SAEs in accordance with the trial risk assessment and protocol.

9.5.3. NCTU

- Assessment of expectedness of any URSEs
- Expedited reporting of URSEs to the Research Ethics Committee (REC) within required timelines
- Notification of all investigator sites of any URSE that occurs
- Responsibility to perform delegated duties as documents in the Safety Reporting Plan with regards to recording, notifying, and reporting safety information.

9.5.4. Trial Steering Committee

The Trial Steering Committee (TSC) will oversee and supervise the progress of the trial to ensure it is being conducted in accordance with applicable guidance and regulations. The TSC will provide overall supervision of the trial on behalf of the Sponsor and Funder. The TSC will help to design the trial and discuss and endorse substantial amendments as appropriate. The TSC will advise on trial progress and ensure regulatory approvals are obtained in line with protocol requirements to maximise the chance of completing the trial in the proposed timescale.

The TSC will consist of an independent Chair and one other clinician with research experience. It will also include the trial CI, trial statistician and lay representatives. Sponsor, Funder and Trial Management Group (TMG) representatives can attend TSCs but do not have voting rights. Other observers may be asked to join TSC meetings for specific discussions where their expertise could be useful.

9.5.5. Data Monitoring Committee

The Data Monitoring Committee (DMC) is independent of the Sponsor and the trial team and is composed of independent members. Although members of these groups can attend DMC meetings. The DMC provides oversight of ethical and safety considerations of patients during the trial.

The DMC has authority to request un-blinded comparative data by treatment group including accumulating safety and outcome data. It is the responsibility of the DMC to ensure participants are not exposed to any excess risk by taking part in the trial. The DMC will report recommendations directly to the TSC and or TMG.

The DMC will consist of at least three independent experienced specialists including at least one clinician who is experienced in the clinical area and at least one statistician.

9.6. Notification of Deaths

Death of a participant taking part in the trial is classified as an SAE and as such will follow the reporting procedures outlined above in section 9.3. All deaths will be reported to the DMC.

9.7. Reporting Urgent Safety Measures

An Urgent Safety Measure (USM) is an action that the Sponsor or an Investigator may take to protect the subjects of a trial against any immediate hazard to their health or safety. An USM may also be used when one arm of a trial shows a clear efficacy over other arm(s) of a trial, and it would be unethical for patients in other arm(s) of the trial to continue on the protocol. If a site identifies an USM they must report this to the NCTU within 24 hours of becoming aware of the USM. This will be done by completing the required sections of the USM Reporting From and emailing it via secure email to the trial manager at the NCTU. The NCTU must inform the NHS REC within 24 hours of the USM being reported and follow up with the REC in writing within three days further outlining the USM and plan of action in accordance with the NCTU's standard operating procedures.

10. STATISTICAL CONSIDERATIONS

10.1. Analysis Population

Patients of all ages with a histologically confirmed diagnosis of intermediate- to high-grade bone or soft tissue sarcoma suitable for curative resection who meet the inclusion and exclusion criteria.

10.2. Statistical Analyses

10.2.1. Analysis of the Primary Outcome Measure

Once margin data has been collected for 250 patients, an interim analysis will be conducted using a Barnard test to calculate a one-sided p-value, with non-binding stopping rules for both overwhelming efficacy and futility with regards to the primary outcome. The final analysis will then occur either after the interim analysis (if the trial stops) with all participants that have been recruited by the time the interim decision is made, or after the full target enrolment is reached (if the trial does not stop). All participants will be followed up for all outcomes, with final data cleaning and database lock occurring after that time. The primary analysis will be based on the Intention-to-treat (ITT) population with all participants included in the group they were randomised to. We do not anticipate a significant number of noncompliance and cross-over issues. If we encounter any protocol deviations or violations related to the treatment allocation, we will also define a perprotocol (PP) population for secondary analyses, in which participants for whom the allocated strategy was not followed will be excluded. All analyses will be described in a Statistical Analysis Plan (SAP) that will be finalised prior to trial statisticians receiving any unblinded data. For the analysis of the primary outcome, UPM rate, we will use a logistic regression that adjusts for key covariates including stratification factors used in the randomisation. A Wald test and a 95% confidence interval will be extracted from this model. A two-sided p-value will be found from the Wald test, although ICG will only be recommended as efficacious if the one-sided p-value for superiority of ICG is <0.0227.

Secondary analyses for the primary outcome will include the per-protocol population and a method that can account for the learning effect such as the hierarchical model approach proposed by Cook

et al ³⁶. Since the UPM rate is measured quickly after randomisation, we anticipate very low missing outcome data. Nevertheless, if this rate is higher than 5%, we will investigate applying a suitable missing at random (MAR) approach such as multiple imputation.

10.2.2. Analysis of Secondary Outcome Measures

Descriptive analysis will be performed to analyse the nature of the data. Secondary outcomes with binary/multiple measures will be analysed with logistic regression. Survival analysis like the Kaplan-Meier statistic will be used to find the overall survival in each arm. For variables with continuous measure, appropriate regression models will be used. Appropriate Statistical tests depending on the nature of the variables (whether qualitative or quantitative) will be used for comparison between the two treatment arms.

10.2.3. Interim Analyses and Criteria for the Premature Termination of the Trial

A non-binding interim analysis will be conducted after margin data for 50% of the target sample size has been achieved. The trial can be terminated if the unexpected positive margin rate is larger in the ICG arm.

10.2.4. Subgroup Analyses

Subgroup analysis will be performed and will be stratified by planned positive margin, sarcoma sub type and treating centre.

10.3. Sample Size Calculations

The reported positive margin rate varies widely in the literature, with quoted values between 8% and 29.9%.^{7,8,10-14} The largest scale paper to have reported UPM rates reported a rate of 9% (n=2217),⁸ although this also included patients with low grade sarcomas, which have lower rates of positive margins,¹⁰ as well as including patients from as far back as 1989, limiting its relevance. Analysis of all patients meeting the trial inclusion criteria between 2010 and 2015 from the North of England Bone and Soft Tissue Tumour Service found an UPM rate of 13.8% (n=224). Data received from two other centres in Europe reported a UPM of 16.3% (n=306). As 13.8% lies between these values, and contains only patients eligible for the trial, this was used for the power calculation. The only published margin rates for patients with intermediate to high grade sarcoma undergoing FGS with ICG is our recent case series, which reported a UPM of 5.1%.³²

As such, figures of 13.8% for the SoC group and 5.1% for the ICG were used for the power calculation. This calculated a sample size of 480 to demonstrate a reduction in the UPM from 13.8% to 5%, at a 1-sided 5% level of significance, with a power of 90%. The sample size of 480 was then inflated to 500 to allow for a modest dropout rate, given the early assessment of the primary outcome.

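### Section 10.3 attaches a one-sided 5% level to 480 patients and 90% power, but neither that sample size nor the 0.0227 decision threshold in 10.2.1 fits that level

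*Protocol*

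**What the plan says.** Section 10.3 (Sample Size Calculations) first states that "figures of 13.8% for the SoC group and 5.1% for the ICG were used for the power calculation". The next sentence gives the result, 480 patients to show "a reduction in the UPM from 13.8% to 5%, at a 1-sided 5% level of significance, with a power of 90" per cent. So the ICG rate appears as 5.1% in one sentence and 5% in the next. Then "The sample size of 480 was then inflated to 500 to allow for a modest dropout rate". Allocation is 1:1 (section 4.1).

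Section 10.2.1 plans one interim analysis once margin data are in for 250 patients. It uses a one-sided Barnard test with non-binding rules for overwhelming efficacy and for futility. The final analysis is a Wald test from a covariate-adjusted logistic regression, and "ICG will only be recommended as efficacious if the one-sided p-value for superiority of ICG is <0.0227".

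The protocol states no overall one-sided level other than the 5% in 10.3, and it gives no numerical interim efficacy boundary.

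**The concern.** Level, power, effect and sample size are tied by arithmetic: any three fix the fourth. The four values in 10.3 do not agree with each other, and the level does not agree with the threshold in 10.2.1.

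Section 10.3 is the only place where the protocol states a significance level for the trial. A reader who relies on it would call a final one-sided p between 0.0227 and 0.05 a positive result, while 10.2.1 says that it is not. Sample-size statements are usually carried into the trial report, so the mismatch invites a dispute over which error rate was prespecified.

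**Working it through.** **Inputs.** p1 = 0.138 (SoC); p2 = 0.050 or 0.051 (ICG, both in 10.3); 1:1 allocation; power 90% (z_β = 1.2816); one-sided level 5% (z_α = 1.6449), all from 10.3. Final threshold one-sided 0.0227 (z = 2.0009) and one look at 250 patients, from 10.2.1.

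**Step 1. The plan's own figure at its stated inputs.** With d = p1 − p2 and p̄ = (p1 + p2)/2, the number per arm is

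- unpooled: (z_α + z_β)² × [p1(1−p1) + p2(1−p2)] / d²
- pooled: {z_α √[2p̄(1−p̄)] + z_β √[p1(1−p1) + p2(1−p2)]}² / d²

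For p2 = 0.051: d = 0.087, p1(1−p1) + p2(1−p2) = 0.11896 + 0.04840 = 0.16736, and 2p̄(1−p̄) = 0.17114. The unpooled form gives (2.9264)² × 0.16736 / 0.007569 = 189.4, so 190 per arm and 380 in total. The pooled form gives 191.8, so 192 per arm and 384 in total. For p2 = 0.050 the totals are 370 and 374.

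Other single-look methods at one-sided 5% and 90% power (5.0% / 5.1%): arcsine 358 / 368; log odds ratio 408 / 418; pooled with continuity correction 418 / 430. An exact Barnard-type test needs about 360 to 380. With an interim look and overall 5%: O'Brien-Fleming 380 / 390, Pocock 416 / 428. None gives 480.

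**Step 2. What 480 patients deliver.** Power at 240 per arm is Φ{(d√240 − z_α √[2p̄(1−p̄)]) / √[p1(1−p1) + p2(1−p2)]}:

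| One-sided level | ICG 5.0% | ICG 5.1% |
|---|---|---|
| 0.05 | 95.3% | 94.9% |
| 0.025 | 91.3% | 90.5% |
| 0.0227 | 90.6% | 89.8% |

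**Step 3. Which input is off?** Total N, unpooled / pooled:

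| Level, power | ICG 5.0% | ICG 5.1% |
|---|---|---|
| 0.05, 90% (as stated) | 370 / 374 | 380 / 384 |
| 0.025, 90% | 452 / 460 | 466 / 472 |
| 0.0227, 90% | 464 / 470 | 478 / 484 |
| 0.05, 95% | 466 / 472 | 480 / 484 |

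The last two rows both reach 480, so the sample size alone cannot show whether the level or the power is misstated.

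**Step 4. The 0.0227 threshold.** Treat the interim and final statistics as bivariate normal with information fraction 250/500 = 0.5, so correlation √0.5 = 0.707. The overall one-sided error is 1 − P(Z1 < z1, Z2 < 2.0009):

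| Interim one-sided boundary | Overall error with final 0.0227 |
|---|---|
| 0.001 | 0.0230 |
| 0.0048 | 0.0250 |
| 0.005 | 0.0251 |
| 0.01 | 0.0284 |
| 0.02 | 0.0358 |
| 0.0227 (same as final) | 0.0379 |
| 0.0373 | 0.0500 |

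To reach 5% overall, the interim boundary would have to be about 0.037, which is easier to cross than the final one. Taking the fraction as 250/480 = 0.52 barely moves this (0.037 to 0.038 for an overall 5%; 0.0048 to 0.0050 for an overall 2.5%). For comparison, the final threshold of an overall one-sided 5% design with one half-way look is about 0.047 (O'Brien-Fleming) or 0.030 (Pocock).

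**Step 5. Does about 2.5% fit everything?** A two-look design with interim 0.0048 and final 0.0227 (overall 2.5%) needs 480 patients for 90% power with 5.1%, and 468 with 5.0%. Level, threshold, power and sample size then agree, and the match is closest with 5.1%.

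**The case against.** Several objections have weight.

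- *The sample size does not identify the error.* True: one-sided 5% with 95% power also gives about 480. A reader might infer that 480 is possible only at 2.5%. Step 3 shows otherwise. It is the 0.0227 threshold that points to the level.
- *A conservative 5% calculation can come close to 480.* Scaling the continuity-corrected 5% totals by the Pocock ratio gives 418 × 416/374 = 465 or 430 × 428/384 = 479. That design's final threshold would be about 0.030, not 0.0227, so the conflict with 10.2.1 stays.
- *The overall 2.5% is inferred.* True. A reader might conclude that the stated error rate is exactly double the real one. The protocol gives neither an overall 2.5% nor an interim boundary, and interim boundaries from 0.001 to 0.01 give 0.0230 to 0.0284. A 5% split with an interim boundary near 0.037 is not impossible, but it does not suit a rule meant for overwhelming efficacy.
- *The interim boundary may be in the SAP.* It may, so its absence is not part of this point. The 3.8% ceiling does not depend on knowing it.
- *The interval.* Section 10.2.1 says that "A Wald test and a 95% confidence interval will be extracted from this model", and a reader might want its level matched to 0.0227. A conventional 95% interval beside a group-sequential threshold is ordinary practice, and the two differ only for one-sided p between 0.0227 and 0.025. This is no error.
- *The operative rule is clear.* Section 10.2.1 leaves no doubt about what will be recommended. This lowers the severity but does not make the statement in 10.3 correct.

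**Conclusion.** The statement in 10.3 is wrong as written. Its inputs call for about 370 to 384 patients (418 to 430 with continuity correction), not 480, and 480 patients at one-sided 5% would have about 95% power, not 90%. A one-sided 5% level also does not fit the 0.0227 threshold: with an interim boundary no looser than the final one, the overall error is at most about 3.8%. An overall level of about 2.5%, with an implied interim boundary near p < 0.005, reconciles all the figures and is the likeliest intention, subject to the sponsor's confirmation.

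The error-rate sums assume one look at about half the information and jointly normal statistics. The protocol's actual tests (Barnard at the interim, adjusted logistic Wald at the end) would shift them somewhat.

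A reader might infer inflated type I error or an underpowered trial. Neither follows: the operative rule is stricter than the stated level, and 480 patients have about 90% power at it. The point should be fixed but is not critical. The alternation between 5% and 5.1% is minor. It moves the total by 10 to 14 patients and does not explain the gap.

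**What to change.** In section 10.3:

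1. Replace the one-sided 5% level with the overall one-sided level actually used. The figures imply about 2.5%; the sponsor is to confirm it from the original calculation.
2. Cite the final-analysis threshold of one-sided 0.0227, so that 10.3 and 10.2.1 describe the same design.
3. Use 5.1% for the ICG arm in both sentences.
4. Restate the power of 480 patients at that threshold: about 90% (89.8% with 5.1%, 90.6% with 5.0%, fixed-sample pooled formula).

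The cost is protocol wording only. The 480 patients, the inflation to 500 and the 0.0227 threshold do not change, and the 95% interval can stay. The correction is best made before the interim analysis, so that no one can suggest that the level was chosen after seeing data.

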11. DATA HANDLING

11.1. Data Collection Tools and Source Document Identification

Data will be collected using Case Report Forms (CRFs), electronic Case Report Forms (eCRFs) selfreport questionnaires, histopathology reports and information taken from participant clinical notes. These will be considered the source documents containing the source data. Data will be transcribed by site staff with delegated responsibility from these source documents onto the eCRFs onto the clinical data management software package, Sealed Envelope Red Pill. Data transferred from site to the secure validated database by remote access will be secure and encrypted. Interventional Non-CTIMP Protocol Template; version 1.0; dated 14 September 2015 SarcoSIGHT

11.2. Data Handling and Record Keeping

Data will be handled, stored, and transferred in accordance with the UK General Data Protection Regulations (GDPR) 2018.

Some patient personal identifiable data will be stored for screening and recruitment tracking purposes. These files will be stored at the recruiting NHS site in a shared trial folder on a secure server. The files will be password protected. Paper copies which include personal identifiable data, such as consent forms and enrolment logs, will be stored in locked rooms and in participants clinical notes. Access to this information will be strictly limited to members of the research team who have been delegated the responsibility.

All participants will be given a unique trial identification (ID) code. All participant trial related data will be connected to this unique ID. Trial data will be collected on paper CRFs and eCRFs. A copy of data collected on paper CRFs will be filed in the participant's clinical notes. Data contained in paper CRFs, data relevant to the trial that has been recorded in participant's clinical notes will be transferred to the secure encrypted password protected trial clinical data management system, Sealed Envelope Red Pill. Pseudonymised image data from the Stryker SPY-PHI camera used during surgery for those participants in the intervention arm will be, where possible, stored at site in a shared trial folder on the NHS server. Pseudonymised images from the Stryker SPY-PHI camera will be uploaded by NHS sites to Newcastle University Secure File Drop Off Service to be retrieved by Database Managers at NCTU. If NHS sites are not able to store pseudonymised images on a shared trial folder on the NHS server or are not able transfer the images to the NTCU via a secure file drop off service, NHS sites can send an encrypted USB stick with the pseudonymised images to NCTU via tracked and recorded delivery. The pseudonymised images will be stored in secure research folders on the Newcastle University server.

11.3. Access to Data

Staff involved in the conduct of the trial, including PIs, recruiting site's delegated trial team, TMG members will have access to trial site files. Access to a participant's personal identifiable data will be strictly limited to delegated members of the research team at the recruiting NHS site. Access to the pseudonymised trial data will be limited to the relevant members of the recruiting site as well as the Sponsor, NCTU, and trial oversight committees such as the DMC and TSC.

Access to Sealed Envelope Red Pill database will be password protected and restricted to a user's particular role and will be limited to a site's PI and their delegated research team members. NCTU's trial management team will have monitor role access to the trial's Red Pill database for all sites for monitoring purposes.

Clinical information will not be released without the written permission of the participant, except as necessary for monitoring and auditing by the Sponsor or its designee, regulatory authorities, the DMC or the TSC.

The PI and trial staff involved in this trial may not disclose or use for any purpose other than performance of the trial, any data, record, or other unpublished, confidential information disclosed to those individuals for the purpose of the trial.

Written agreement from the Sponsor or designee must be obtained before the disclosure of any confidential information to other parties.

Until publication of the trial results, access to the full dataset will be restricted to the Trial Management Group and to authors of the publication.

